Coprimary efficacy endpoints will be used to test the hypothesis that surgical site infiltration with LB is non-inferior to TEA: (1) the mean Area under the Curve (AUC) of visual analog scale (VAS) pain intensity scores from 0 to 48 hours postoperatively and (2) total opioid consumption (IV morphine equivalents, mg) from 0 to 48 hours postoperatively will be compared between the two treatment groups. The mean AUC of VAS pain intensity scores endpoint incorporates the use of rescue medications by using an imputation method called windowed worst observation carried forward (WWOCF). This method imputes a subject's pain score as their worst pain score for a pre-specified window after a rescue medicine. Subjects will be evaluated for pain intensity at rest at 6, 12, 18, 24, 30, 36, 42, 48, and 72 hours after surgery and then once daily (at noon \pm 4 hours) through postoperative day 14. Subjects will also record an unscheduled pain score immediately before any requested opioid pain medication. The exact time of the assessment will be recorded to limit variability. Total opioid consumption in IV morphine equivalents (mg) during the first 48 hours postoperatively will be tracked for each subject.

Secondary objectives:

To compare the impact of TEA and surgical site infiltration with LB on patient reported and clinical outcomes as well as on neuroendocrine and inflammatory mediators of the surgical stress response using the following measures:

1. Mean patient-perceived quality of recovery score on postoperative days 1-7 (QoR-15).
2. Time to return of bowel function (ROBF) and incidence of postoperative ileus.
3. Mobility Level.
4. Degree of sedation.
5. Length of hospital stay and time (in days) to meeting discharge criteria.
6. Total intravenous fluids administered and time to postoperative diuresis.
7. Need for vasopressors (amount and duration).
8. Incidence of major postoperative complications, including 30-day hospital readmission.

9. Total direct costs associated with loco-regional anesthesia.
10. Post-discharge narcotic utilization.

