1. Mean patient-perceived quality of recovery score on postoperative days 1-7. Patient-perceived quality of recovery will be assessed using the Quality of Recovery score (QoR-15) which is a validated instrument designed to measure the major domains of postoperative recovery including functional independence, physical comfort/pain, psychological/emotional well-being, cognition and satisfaction (Appendix A). Quality of recovery will be measured using this instrument on the first postoperative day and each day thereafter (at noon \pm 4 hours during a period of rest) during inpatient hospitalization to and including the day of discharge or postoperative day 7 (whichever comes first) in order to obtain longitudinal data about the quality of recovery experienced by patients. Patients unable to complete the questionnaire independently will be asked for verbal responses to each item.

2. Time to return of bowel function (ROBF) and incidence of postoperative ileus. Time to ROBF will be defined as the time lapse from the day of surgery (DOS) to the day oral intake is tolerated for 48 hours without vomiting. Ileus is defined as the occurrence of postoperative nausea and vomiting requiring cessation of oral intake and initiation of intravenous hydration +/- nasogastric tube placement following documented ROBF or the persistence of these symptoms beyond postoperative day 5 in the absence of ROBF.

3. Level of mobilization. Preoperative baseline mobility will be assessed using the Boston University AM-PAC Surgical Short Form per our standard practice. On the first postoperative day and each day thereafter through date of discharge or postoperative day 7 (whichever comes first), mobility will be assessed using the 8-point validated JH-HLM scale. Need for formal physiotherapy consultation will also be recorded.

4. Degree of sedation. Degree of sedation will be assessed on each postoperative day through the date of discharge or postoperative day 7 (whichever comes first) at noon \pm 4 hours using the Pasero Opioid Induced Sedation Scale (Appendix B).

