5. Length of hospital stay and time (in days) to meeting discharge criteria. Often, patients remain inpatient beyond the time at which they first meet discharge criteria due to a variety of psychosocial factors. Thus, length of hospital stay and time (in days) to meeting discharge criteria will be separately recorded. Discharge eligible criteria include: (1) hemodynamically stable, (2) afebrile, (3) ROBF, (4) pain controlled with oral analgesics, (5) independence with ADLs, (6) walking greater than 250 feet.

6. Total intravenous fluids administered and time to postoperative diuresis defined as the time lapse from date of surgery (DOS) to a net negative fluid balance sustained over a 24 h time period.

7. Need for vasopressors (amount and duration).

8. Incidence of major postoperative complications, including 30-day hospital readmission.

9. Total direct costs associated with loco-regional anesthesia: The analysis will include the direct variable cost of supplies and pharmacy (including initiation of PCA in the event of block failure) as well as anesthesia professional fees (TEA only; both intraop and postop) and cost of OR time in minutes to perform the blocks.

10. Post-discharge narcotic utilization. Total outpatient narcotic use during the immediate outpatient postoperative period will be obtained from the patient by nurse phone survey on postoperative day 14, provided the patient is outpatient and not still admitted or readmitted to the hospital.

Translational Endpoints:

1. Biomarkers of surgical stress response. Blood samples (10mL of whole blood) will be collected on the DOS when routine IV access is established in preop or the operating room and postoperative days 1 through postoperative day 7 coinciding with routine IV access for blood, for analysis of peripheral blood counts. Blood collection on postoperative day 0 is optional. Serum will

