Many randomized controlled trials over the past 20 years have focused on the benefits of TEA. TEA is effective in attenuating the surgical stress response and reducing pain and opioid consumption for up to 72 hours (h) following abdominal incisions, and also has an impact on complications following abdominal surgery, reducing the time to bowel recovery by up to 36 h and may reduce cardiac and respiratory complications in high-risk patients.⁶⁻⁸ While analgesia and recovery seem to be better with TEA than intravenous opioid patient controlled analgesia (PCA), the role of TEA in pain control for patients on ERAS programs following open gynecologic and colorectal surgery is controversial. TEA failure rates are as high as 30% and many of these patients will require supplemental opiates.⁹ The sympathetic block that results from TEA commonly results in hypotension that results in at least temporary discontinuation of the infusion, prompts intravenous fluid administration to already volume overloaded patients and may require treatment with vasopressors.¹¹ TEA may hinder achievement of other ERAS goals such as mobilization and removal of urinary catheters, and TEA has been shown to increase length of hospital stay and complication rates in gynecologic cancer surgery.^{12, 13}

Given these disadvantages, some leading ERAS programs use surgical site infiltration with long acting local anesthetics in lieu of TEA. Extended-release liposomal bupivacaine (LB) was recently approved by the FDA for single-dose surgical site infiltration to produce postsurgical analgesia. The liposomal preparation consists of microscopic multi-vesicles with a lipid-soluble lining and an aqueous core containing encapsulated bupivacaine allowing it to be slowly released over a period of up to 72–96 h.¹⁴ Existing data indicate that surgical site infiltration with LB following mastoplasty and open colectomy decreases postoperative opioid requirements and length of stay.^{15, 16} Recently, the Mayo Clinic published their

experience with abdominal incision injection of LB versus standard bupivacaine hydrochloride after laparotomy for gynecologic malignancies. Compared to bupivacaine hydrochloride, abdominal incision infiltration with LB was associated with less opioid consumption as well as lower rates of postoperative nausea and ileus. Pain scores, length of hospital stay and total pharmacy costs did not differ between the groups.¹⁷

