Intention to treat statistical analyses will be used to test the null hypothesis. Thus, if a patient has been randomized to the TEA arm of the trial and an epidural cannot be placed or cannot be used due to other circumstances (ie. persistent hypotension) the patient will receive the other elements of the ERAS multimodal pain bundle, which is consistent with our current clinical practice and that patient's data will be included in the dataset for the TEA arm in the final analysis. Additionally, in the event a participant wishes to drop out of the study prematurely postoperatively (ie. declines further blood/saliva collection and/or to fill out surveys), they will be allowed to do so and the data collected during their enrollment period will still be included in the dataset for their respective treatment arm unless they submit a formal written objection.

Secondary outcome variables:

T-tests or the nonparametric Mann-Whitney test will be used to compare normally and non-normally distributed data between the study arms. The log-rank test will be used to compare the time to (ROBF) as well as the time to postoperative diuresis to account for right censoring in which case no event (ROBF/diuresis) is observed within the observed time. A Poisson regression model will be used to compare the length of hospital stay. Chi-square tests will be used to compare the incidence of major postoperative complications between the two treatments. Chi-square tests will also be used to compare the incidence of major postoperative complications between the two treatments. Daily mean and median as well as mean baseline change in surgical stress biomarkers will be compared between treatment groups using t-tests or the Mann-Whitney test depending on whether data are normally or non-normally distributed. Average daily QoR-15 scores will be compared between the study cohorts.

b. Early stopping rules.

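### QoR-15 is named as a mean over days 1-7 but collected only until discharge, so the comparison between arms is confounded by length of stay

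*Combined protocol and SAP*

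**What the plan says.** Section 2 (Secondary objectives) lists as item 1 "Mean patient-perceived quality of recovery score on postoperative days 1-7 (QoR-15"). The fuller description of the item schedules the questionnaire daily from the first postoperative day "during inpatient hospitalization to and including the day of discharge or postoperative day 7 (whichever comes first) in order to obtain longitudinal data". Section 4a repeats that cut-off.

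Section 7a (Secondary outcome variables) opens with a general choice between t-tests and Mann-Whitney tests. On this endpoint it says only: "Average daily QoR-15 scores will be compared between the study cohorts". It gives no summary rule, no model, and no treatment of days after discharge.

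Length of stay is a secondary outcome in its own right: "A Poisson regression model will be used to compare the length of hospital stay". Section 2, item 5 sets the conditions for discharge. They include return of bowel function, a walking distance, and "4) pain controlled with oral analgesics, (5) independence with ADLs".

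On the likely difference in stay, Section 3 (Background) says that "TEA has been shown to increase length of hospital stay and complication rates in gynecologic cancer surgery". The same paragraph credits thoracic epidural analgesia (TEA) with "reducing the time to bowel recovery by up to 36 h". It gives no number of days for the effect on stay.

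For post-discharge opioids, Section 2, item 10 says: "Total outpatient narcotic use during the immediate outpatient postoperative period will be obtained from the patient by nurse phone survey on postoperative day 14". This applies only if the patient is not in hospital at that point.

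**The concern.** For any patient who goes home before day 7, the endpoint as named cannot be calculated. What can be calculated is a mean over a number of days that the patient's own discharge decides. Discharge depends on pain control, independence and walking, which overlap the functional and pain domains that QoR-15 measures. The missing days are therefore not a random subset.

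Section 7a allows two readings, and both have the problem. A per-patient mean weights early leavers towards the first days after surgery. A comparison day by day sets the not-yet-discharged of one arm against the not-yet-discharged of the other, and these are differently selected groups if stays differ.

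Post-discharge narcotic use has the same root in mirror form. Its window opens at discharge, so an earlier discharge adds days to the total, and patients who are still admitted or readmitted contribute nothing.

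At stake is the interpretation of the first-listed patient-reported outcome. Home scores that were never collected cannot be recovered later.

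**Working it through.** The documents state no figure for QoR-15 or post-discharge opioid use, so there is none to reproduce.

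**Inputs.** From the documents: the collection window, the discharge criteria, and the day-14 call. Not in the documents, and therefore assumed: the daily change in QoR-15, length of stay by arm, and the course of opioid use.

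**1. Per-patient mean, identical recovery in both arms.** Let the score on day t be a + s·t. The mean over days 1 to d is a + s(d+1)/2. If one arm stays D days less than the other, both within day 7, the difference in means is −s·D/2, although the true difference is 0.
- Discharge on day 3 or day 4: the mean observed day is 2.0 or 2.5, so the gap is 0.5·s.
- D = 1: s = 3 gives −1.5 points and s = 8 gives −4.
- D = 2: s = 3 gives −3 points and s = 8 gives −8.
- s = 0 gives 0. With s = −2 the sign reverses: +1 for D = 1, +2 for D = 2.

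**2. Both readings of the analysis, simulated.** There were 100,000 patients per arm, with starting level 90 (SD 12) and mean slope 5 per day (SD 1.5). Discharge came when the underlying score reached 112, never before day 2. Recovery was the same in both arms, but the TEA arm was held 1 or 2 days longer. All of these values are assumed.

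| TEA held longer by | Per-patient mean, LB − TEA | Inpatients day by day, from day 3 |
|---|---|---|
| 1 day | −2.0 | −2.6 to −3.9 |
| 2 days | −3.5 | −3.8 to −7.6 |

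The per-patient values are smaller than s·D/2 (2.5 and 5.0). Part of the reason is that the day-7 limit cuts the gap in observed days to 5.52 − 4.82 = 0.70 and 6.10 − 4.81 = 1.29. Days 1 and 2 show no bias, because nobody could leave before day 2.

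**3. The arm that leaves sooner truly recovers faster.** The discharge rule was the same, with no extra holding time, and LB had the steeper slope.

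| Slopes, LB and TEA | True 7-day difference | Seen with collection to discharge | Share lost |
|---|---|---|---|
| 6 and 5 | 4.0 | 1.5 | 1 − 1.5/4.0 ≈ 63% |
| 7 and 5 | 8.0 | 2.6 | 1 − 2.6/8.0 ≈ 68% |

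With all seven days collected, the artefact in steps 1 and 2 is 0 by construction, and the true differences in step 3 are recovered.

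**4. Post-discharge opioid total, identical daily use.** The window is 14 minus length of stay.
- Stay of 3 against 4 days: 11 against 10 outpatient days. The ratio of totals is 11/10 = 1.10 with constant use, and 1.37 if use declines at a rate of 0.3 per day.
- Stay of 4 against 6 days: 10 against 8 outpatient days. The ratio is 1.25 with constant use, and 1.90 with the same decline.
- A window fixed from surgery, the same for every patient, gives 1.00.

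**The case against.** **Direction.** A reader might infer that the bias must run against LB because TEA prolongs stay. The documents do not go that far. The Background cites prior evidence of longer stay without a number of days, and also cites faster bowel recovery with TEA. Return of bowel function is a discharge criterion. No QoR-15 trajectory is given either. This objection stands: the direction is conditional.

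**Severity of distortion.** A reader might also infer that a true LB benefit could appear as harm. In the cases worked above it shrinks and does not reverse. An apparent deficit arises where recovery is equal but stay differs. Because the discharge criteria are themselves recovery measures, equal recovery would tend to give equal eligibility. Stay can still differ for other reasons: the Background says that TEA may hinder mobilisation and catheter removal, and Section 2 notes that patients often stay after meeting the criteria.

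**Limited reach.** The first two days should be largely intact, length of stay and time to discharge criteria are recorded separately, and this is one of ten secondary measures with no decision rule. All true, but none of it supplies the mean over days 1-7 that the plan names. A likelihood-based model might recover part of it if discharge depended only on recorded scores, but the plan specifies no such model.

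**Opioids.** Outpatient opioid exposure is a legitimate question, given the plan's stated concern with opioid dependence. More outpatient days is then part of what is measured, so the endpoint need not be replaced. Nor is 10% more days necessarily 10% more opioid. The objection does not answer the omission of patients in hospital or the lack of a comparison over equal time.

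**Conclusion.** The fault is structural and holds on the text. The named endpoint and the collection window do not match, the cut-off is an outcome that treatment may affect, and the analysis sentence does not repair this on either reading.

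The size depends on assumptions: 1.5 to 4 points per day of difference in stay, for an assumed linear rise of 3 to 8 points per day, identical recovery, and discharge within day 7. Where the arm that leaves sooner truly does better, about 60-70% of its benefit was lost in the simulated cases. The documents give no SD or important difference for QoR-15, so clinical importance cannot be judged from them. The disadvantage falls on whichever arm leaves sooner, provided scores rise. That this arm is LB is plausible from the Background but not established.

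The co-primary endpoints over 0-48 hours are not affected. The post-discharge narcotic total is usable as a description of outpatient use. It should not be read as a like-for-like comparison of opioid need between arms.

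**What to change.** 1. **Collection (Section 2, item 1, and Section 4a).** Collect QoR-15 daily through day 7 regardless of discharge, self-completed at home alongside the pain score already recorded through day 14 in the same noon ± 4 hour window.
2. **Analysis (Section 7a).** Specify a repeated-measures mixed model with treatment, day, treatment × day and the randomisation stratum (suspected malignancy).
3. **Fallback.** If home collection is not adopted, restrict the between-arm comparison to early days, such as days 1-2, when nearly all patients should still be inpatients. The plan's own criteria support this: discharge needs return of bowel function, defined through 48 hours of tolerated oral intake.
4. **Opioids.** Keep post-discharge narcotic use as descriptive. Add total opioid use from 48 hours to day 14 for every patient, including those still admitted or readmitted, from the medication administration record plus the day-14 survey or the outpatient medication logs.

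**Cost.** A protocol amendment and a few extra forms per patient: a patient discharged on day 3 would complete 7 − 3 = 4 at home. No visit is added. The documents describe no daily staff contact after discharge, so the forms must be self-completed. Patients who need the items read aloud would need a call, and some home forms will be missing.

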- c. Justification and safety information if non-FDA approved drugs without an IND will be administered.

7. Study Statistics

- a. Primary outcome variables:

The study has two co-primary endpoints: (1) the mean Area under the Curve (AUC) of visual analog scale (VAS) pain intensity scores from 0 to 48 hours postoperatively and (2) total opioid consumption (IV morphine equivalents, mg) from 0 to 48 hours postoperatively. The primary hypothesis will be assessed in joint hypothesis testing which controls the type I error at 0.025 across both non-inferiority tests; AUC for VAS pain scores and total opioid consumption through 48 hours postoperatively. Significance will need to be achieved for both co-primary endpoints.

For analyzing the AUC of the VAS pain assessment, we will use an approach that has been previously used in Pacira studies. The area under the curve (AUC) is derived using the trapezoidal rule (see formula below) using the adjusted and imputed VAS pain scores. The VAS scores will be adjusted for the use of rescue medication using the WWOCF approach. AUC will start with the first postsurgical pain assessment. All pain assessments through 48 hours after surgery, including both scheduled and unscheduled will be used in deriving AUC. Exact assessment times will be used in deriving AUC.

$$AUC = \left\{ \sum_{i=2}^n (p_i + p_{(i-1)})(t_i + t_{(i-1)}) \right\} / 2$$

The AUC for VAS may be analyzed using ANOVA with treatment group as a main effect and include other covariates as deemed reasonable. Based on the model, the LS Mean and SE will be reported for each treatment group. The 95% confidence interval for the difference between

treatment groups and the one-sided test performed at 2.5% level of significance will be inspected for non-inferiority.

Total opioid consumption over 48 hours postoperatively will be abstracted by our research assistant from the medical administration record (MAR) as it appears in the EMR for each patient.

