The analysis of total opioid consumption over 48 hours is based on an approach that has been used previously in Pacira studies. For the endpoint total opioid consumption (IV morphine equivalents, mg) from 0 to 48 hours postoperatively, opioid dose will be converted to IV morphine equivalent dose using the conversion factor from the table below. The endpoint will be the summation of all opioids taken post-surgery through 48 hours. Subjects with no opioid use during the period in question will be assigned a dose of 0 mg for summaries.

The total opioid consumption through 48 may be analyzed using ANCOVA with treatment group as a main effect and include other covariates as deemed reasonable. Based on the model, the LS Mean and SE will be reported for each treatment group. The 95% confidence interval for the difference between treatment groups and the one-sided test performed at 2.5% level of significance will be inspected for non-inferiority. The data may be natural log transformed.

Medication	Unit	Route	IV Morphine Conversion Factor
Duramorph	mcg	IT	0.1
Oxycodone, Oxycocet, Percocet, acetaminophen-oxycodone	mg	PO	0.5
Morphine	mg	IV, IM, SC	1
Morphine	mg	PO	0.33
Hydromorphone (Dilaudid)	mg	IV, IM, SC	6.67
Hydromorphone (Dilaudid)	mg	PO	1.3
Fentanyl	mg	IV, PO, IM	100
Hydrocodone combination product - Vicodin, Norco, Lorcet, Lortab, hydrocodone-acetaminophen, Ketobemidone	mg	PO	0.33
Codeine combination product - Tylenol 3, acetaminophen-coedine, Paracetamol Forte, Tylenol 4	mg	PO	0.05
Ultram, Tramadol, Tramadol hydrochloride	mg	PO, IM	0.08
Demerol, Meperidine, Pethidine	mg	IV, SC	0.1
Demerol, Meperidine, Pethidine	mg	PO	0.033
Ketobemidone, Oxycodone	mg	IV	1

Regarding the non-inferiority margin for the total opioid endpoint, previous literature indicated a difference of 10.6mg IV morphine equivalent dose daily is a clinical different threshold [24]. Therefore, total opioid consumption through 48 hours for LB treatment group is to be no more than 21.2 IV (10.6 x 2 Days) morphine equivalent doses greater than the total opioid consumption through 48 for TEA treatment group. It may be reasonable to apply a natural log transformation, in which case the NIM threshold will be adjusted accordingly.

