The study is powered for the primary outcome of Area under the Curve (AUC) for pain from 0-48 hours. From review of the literature of previous studies, we deemed a margin of 80% of 48 hours to be non-inferior [24,25,]. A group sample size of 50 per cohort is needed achieve a 90% power to detect non-inferiority using a one-sided, Mann-Whitney test. The margin of non-inferiority is 38 (80% of 48 hours). The non-inferiority margin corresponds to an increase in pain, not a decrease. The pain VAS ranges from 0 to 10, with 10 being the worst pain. Therefore, non-inferiority will be declared if the average AUC for liposomal bupivacaine is no more than 38 units compared to the average AUC in the TEA group. The true difference between the means is assumed to be 0.0. The significance level (alpha) of the test is 0.025 and the data are drawn from populations with standard deviations of 55.0. These assumptions were derived from previous Pacira studies. It is reasonable to assume that the standard deviation of the AUC for 0-48 hours is about 55 units and the difference between the groups is 0. Sample size calculations were performed using PASS (PASS 16 Power Analysis and Sample Size Software (2018). NCSS, LLC. Kaysville, Utah, USA, ncss.com/software/pass). Of note, with sequential testing of the co-primary endpoints, the study remains to be adequately powered with the addition of the total opioid consumption co-primary endpoint. A sample size of 50 participants in each arm will have adequate power (>90%) to detect non-inferiority with a margin of 21.2 IV morphine equivalents using a one-sided test with a common standard deviation of 25 and alpha of 0.025. The non-inferiority margin was determined by the clinically significant threshold of 10.6 mg in daily IV morphine equivalent dose [24], therefore, 21.2 morphine equivalent dose for over 2 days (0-48 hours).

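### The mobility comparison has no prespecified use of the preoperative AM-PAC score or the malignancy stratum, although adjusting for both costs almost nothing and may sharpen the estimate

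*Combined protocol and SAP*

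**What the plan says.** Section 2, secondary endpoint 3, sets the preoperative measurement, made as part of routine practice: "Preoperative baseline mobility will be assessed using the Boston University AM-PAC Surgical Short Form". From the first postoperative day until discharge, or day 7 if that is earlier, "mobility will be assessed using the 8-point validated JH-HLM scale".

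Section 7, under Secondary outcome variables, opens with a general rule: "T-tests or the nonparametric Mann-Whitney test will be used to compare normally and non-normally distributed data between the study arms". It then gives methods for return of bowel function, diuresis, length of stay, complications and biomarkers, and mentions QoR-15. Mobility is not named, and nothing says how up to seven daily scores per patient are to be combined.

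Baseline values and covariates do appear elsewhere in Section 7. For biomarkers, "Daily mean and median as well as mean baseline change in surgical stress biomarkers will be compared between treatment groups". For the first co-primary endpoint, "The AUC for VAS may be analyzed using ANOVA with treatment group as a main effect and include other covariates as deemed reasonable"; the opioid endpoint "may be analyzed using ANCOVA with treatment group as a main effect and include other covariates as deemed reasonable". Randomisation is stratified by suspected malignancy (Section 4a), but the mobility comparison does not use that stratum.

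**The concern.** A preoperative measure of the same construct is on file for each patient, yet no analysis is said to use it. A change score is not available, because the two instruments differ. Covariate adjustment is therefore the natural way to use the baseline, and the general rule has no place for a covariate.

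The outcome is of real interest. The Background (Section 3) suggests that TEA may impede mobilisation, and the discharge criteria in Section 2 include a walking distance of more than 250 feet. Randomisation is stratified only on suspected malignancy, so preoperative function is balanced by chance alone. The trial is open-label, so an adjustment chosen after the data have been seen would be open to challenge; one fixed in advance would not.

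**Working it through.** **Inputs from the documents.** 50 per arm, 1:1 allocation; AUC margin 38, SD 55, true difference 0, one-sided alpha 0.025, power 90% (Sections 4a and 7). No SD, target difference, power or alpha is given for mobility.

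**Assumed inputs.** The correlation r between AM-PAC and JH-HLM, shown as a range from 0 to 0.7. Two-sided alpha 0.05 and 80% power for the detectable difference. JH-HLM treated as one continuous score per patient.

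**Step 1: the plan's own figure.** The plan states "A group sample size of 50 per cohort is needed achieve a 90% power to detect non-inferiority using a one-sided, Mann-Whitney test". By the normal approximation, n = 2 × (1.960 + 1.282)² × 55² / 38² = 44.0, so 45 per arm. The noncentral t gives 46. Multiplying by π/3 for the Mann-Whitney test under normal data gives 48. At 50 per arm, power is 0.932 (normal), 0.928 (t) and 0.916 (Mann-Whitney, simulated). The stated 50 is reproduced. It concerns pain AUC and carries no information about mobility.

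**Step 2: precision of the mobility comparison.** With one baseline covariate, the residual variance is multiplied by 1 − r², the standard error by √(1 − r²), and the equivalent unadjusted sample is 50 / (1 − r²) per arm. The unadjusted detectable difference is (1.960 + 0.842) × √(2/50) = 0.560 SD; adjustment multiplies it by √(1 − r²).

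| Assumed r | Variance reduction | SE reduction | Equivalent n per arm | Detectable difference (SD) |
|---|---|---|---|---|
| 0 | 0% | 0% | 50 | 0.560 |
| 0.1 | 1% | 0.5% | 50.5 | 0.558 |
| 0.2 | 4% | 2.0% | 52 | 0.549 |
| 0.3 | 9% | 4.6% | 55 | 0.535 |
| 0.5 | 25% | 13.4% | 67 | 0.485 |
| 0.7 | 49% | 28.6% | 98 | 0.400 |

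**Step 3: cost of adjusting.** Estimating one covariate effect with 100 patients inflates the standard error by about √(1 + 1/96) = 1.005, that is 0.5%. At r = 0 this is a net loss of 0.5%; at r = 0.1 it cancels the gain; at r = 0.3 it leaves 4.1% and at r = 0.5 it leaves 12.9%. A stratum term uses one further degree of freedom, a cost of the same order.

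**Step 4: chance imbalance.** The standardised difference in baseline between arms has SD √(2/50) = 0.20, so about 1 trial in 20 exceeds 1.96 × 0.20 = 0.39 SD in either direction. An imbalance of that size shifts the expected unadjusted mobility difference by r × 0.39: about 0.12 SD at r = 0.3 and 0.20 SD at r = 0.5. Adjustment removes this shift.

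**Step 5: when observation stops.** JH-HLM is recorded only until discharge or day 7. The discharge criteria include walking more than 250 feet and independence in daily activities. Follow-up of the outcome therefore ends in a way that depends on the outcome, and any analysis over days 1 to 7 must say what it does with the days after discharge.

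**The case against.** The strongest reply is that this is an efficiency option, not an error. Allocation is random, so the unadjusted comparison is valid. Mobility is one of ten secondary measures, with no power target. The AM-PAC form is collected as routine practice, so nothing is wasted if it only describes the arms at baseline. All of that stands, and it is why the point is minor.

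Four stronger readings are tempting, and the documents do not support them.

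- A reader might infer that precision is certainly lost because preoperative function predicts mobility strongly. No correlation, and no data from which to derive one, is given, and at r of 0.1 or less nothing is lost.
- A reader might take the change of instrument as the defect. The plan never promises a change score for mobility, and a covariate need not be on the same scale as the outcome.
- A reader might say that the plan chose an unadjusted mobility test. That is inferred from a general sentence; mobility itself is not named.
- A reader might infer bias. Randomisation rules that out on average; what remains is chance imbalance in a single trial.

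It is also fair to say that the 1 − r² figures describe linear ANCOVA on one score. They are only a guide for an ordinal or repeated-measures model of an 8-point scale.

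What survives is that a baseline already collected and a stratum already used in randomisation have no stated role in the comparison, and that giving them one costs almost nothing.

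**Conclusion.** The point holds as a modest improvement to a secondary analysis. The only rule that applies to mobility is unadjusted, and neither AM-PAC nor the malignancy stratum enters it. The possible gain from AM-PAC runs from nothing (r of 0.1 or less) through 9% lower variance at r = 0.3 to 25% at r = 0.5, against a cost of about 0.5% of the standard error if the covariate proves useless. These figures rest on an assumed r, a linear approximation and all 50 patients per arm contributing a score. No gain was calculated for the stratum. The documents do not allow the actual gain to be computed, and they do not show the unadjusted result to be biased. Neither co-primary conclusion is affected, and the sample size stands.

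**What to change.** In Section 7, under Secondary outcome variables, name the mobility analysis: JH-HLM compared between arms by linear or ordinal regression, adjusted for baseline AM-PAC score and malignancy stratum, with the adjusted arm difference and its confidence interval reported.

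State also which JH-HLM outcome is modelled. There are two workable choices:

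- one fixed early postoperative day on which most patients are still inpatients, chosen before any comparison by arm; or
- a repeated-measures model over the daily scores, with an explicit rule for days after discharge, because discharge depends on mobility.

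The cost is a few sentences in the plan and, in the analysis, one or two degrees of freedom. No new data, visits or patients are needed.
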